9.2. Missing Data

No imputation of missing data will be made. If any questionnaire (e.g., AKSS) has a missing item, the total score for that scale will be considered missing.

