3.2. Number of Subjects

RSA is able to measure wear with high accuracy. Previous RSA wear studies show that the expected wear rate is 0.13 ± 0.08 mm a year (Short et al., 2005; Kellett et al., 2004). A clinical relevant difference to detect differences in wear would be a standard deviation of 0.1 mm a year.

Group sample sizes of 27 patients in each group would achieve 95% power to detect a difference of -0.1 mm wear between the null hypothesis that both group means are 0 and the alternative hypothesis that the mean of group 2 is 0.1 with estimated group standard deviations of 0.1 and with a significance level (alpha) of 0.05 using a two-sided two-sample t-test.

However, in order to also achieve the third objective of this protocol whereby clinical parameters will be correlated with RSA results, more patients are needed to obtain stronger correlations with the important

clinical outcome parameters. Taking the latter in account and to compensate for possible lost to follow up, 50 patients will be recruited per study group.

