6.1. Study parameters/endpoints

6.1.1 Clinical outcome

- Relief of Pain, measured by an increase in the pain score component of the Knee Society Score
- Restoration of Function, measured by an increase in the functional score of the Knee Society Score.
- Patient satisfaction as determined by answers to patient outcomes questionnaires (EQ 5-D, SF-36 and Lower Extremity Activity Scale).

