6.1.3 Patient success or failure

Each patient from the two groups must meet the following criteria at the two-year (± 2 months) evaluation in order to be considered as “success”:

Patient Success - defined by the following requirements at the two-year follow-up interval:

- A Knee Score of ≥ 80, and
- No component revisions or removals (femoral, bearing, tibial or patella), and
- No pending component revisions or removals (femoral, bearing, tibial or patella) and
- Absence of Osteolysis in any component (femoral, bearing, tibial or patella) and
- No migration / subsidence of >3mm or >3° in any component (femoral, bearing, tibial or patella)

A patient who meets any of the following criteria at the two-year (\pm 2 months) evaluation will be considered as “failure”:

Patient Failure – defined by the following requirements at the two-year follow-up interval:

- A Knee Score of < 80 , or
- Revisions or removals of any component (femoral, bearing, tibial or patella), or
- Pending revisions or removals of any component (femoral, bearing, tibial or patella), or
- Presence of Osteolysis in any component (femoral, bearing, tibial or patella), or
- Migration / subsidence of 3 mm or $>3^\circ$ in any component (femoral, bearing, tibial or patella).

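### One blank item voids a scale's total score with no imputation, so answered items are discarded for secondary scores, and two-year success has no rule for a missing Knee Score

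*Combined protocol and SAP*

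**What the plan says.** Section 9.2 consists of two sentences. The first is "No imputation of missing data will be made". The second is "If any questionnaire (e.g., AKSS) has a missing item, the total score for that scale will be considered missing". What counts as a scale is not defined for any instrument. No partial-score rule and no sensitivity analysis for missing data is given.

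The scores concerned are used in three places:

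- **Section 6.1.1.** Pain is the pain component of the Knee Society Score and function is its functional score. The third outcome is "Patient satisfaction as determined by answers to patient outcomes questionnaires", namely EQ-5D, SF-36 and the Lower Extremity Activity Scale.
- **Section 6.1.3.** "Patient Success - defined by the following requirements at the two-year follow-up interval" introduces a list joined by *and*, which includes a Knee Score of at least 80. The failure list is joined by *or*: a score below 80, revision, pending revision, osteolysis or excess migration.
- **Sections 2 and 3.2.** The third objective correlates clinical scores with RSA results. This is one of the two reasons given for enlarging the trial until "50 patients will be recruited per study group"; the other is loss to follow-up.

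**The concern.** The rule is explicit. A patient who answers all but one item of a scale contributes nothing to that scale at that visit, although most of the information has been collected. Part of the recruitment above 27 per group was justified by the clinical correlations, and this rule gives some of that gain away.

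Section 6.1.3 has a second problem. Success cannot be shown without the Knee Score, but failure can be reached without it. A patient whose score is void and who meets every other criterion has no defined status, while one who fails on another criterion is still counted. If patients without a status are simply left out, successes are lost at a higher rate than failures.

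**Working it through.** **1. The plan's own figure.** Section 3.2 says "Group sample sizes of 27 patients in each group would achieve 95% power to detect a difference of -0.1 mm wear", with "estimated group standard deviations of 0.1" and a "significance level (alpha) of 0.05 using a two-sided two-sample t-test". The noncentral t calculation with difference 0.1, SD 0.1 and 27 per group gives power 0.950, so the figure reproduces. With 50 per group, power is 0.999. Wear is measured by RSA, so section 9.2's item rule does not enter this calculation.

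**2. Share of scores lost.** With k items and an independent blank rate p per item, the share lost is 1 − (1 − p)^k. The documents give no p, so the range is an assumption. Section 6 lists seven AKSS elements. I assume four belong to the Knee Score (pain, motion, stability, alignment) and three to function (walking, stairs, aids). The 10-item scale is illustrative, and 36 items is taken from the name SF-36.

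| Scale | p = 0.5% | 1% | 2% | 5% |
|---|---|---|---|---|
| Function, 3 items | 1.5% | 3.0% | 5.9% | 14.3% |
| Knee Score, 4 items | 2.0% | 3.9% | 7.8% | 18.5% |
| AKSS total, 7 items | 3.4% | 6.8% | 13.2% | 30.2% |
| 10-item scale | 4.9% | 9.6% | 18.3% | 40.1% |
| All 36 items as one scale | 16.5% | 30.4% | 51.7% | 84.2% |

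Example: 1 − 0.99^7 = 0.068. At a fixed average p, blanks that cluster within patients spoil fewer forms, so these are upper bounds if clustering occurs.

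Section 6.1.1 defines pain and function by an increase, so function needs a complete score at two visits: 1 − (1 − p)^(2 × 3) = 5.9% lost at p = 1% and 11.4% at p = 2%.

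**3. Cost in precision, 7-item total, before dropout.** The number left per group is 50(1 − p)^7 = 48.3, 46.6, 43.4 or 34.9. The difference detectable with 80% power (two-sided 0.05) is 0.57 SD at 50 per group. At 48, 46, 43 and 34 (rounded down) it is 0.58, 0.59, 0.61 and 0.69 SD. For an assumed correlation of 0.3, power (Fisher z) is 86% at n = 100, and 84%, 81% and 72% at n = 93, 86 and 70.

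**4. Two-year success.** Let s be true success, f the share failing on a non-score criterion, and q the share of Knee Scores void, unrelated to outcome. If unclassifiable patients are left out, observed success is s(1 − q) / [(1 − f)(1 − q) + f]. With assumed s = 0.80 and f = 0.10:

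- q = 0.07: 0.744 / 0.937 = 79.4%
- q = 0.13: 0.696 / 0.883 = 78.8%
- q = 0.30: 0.560 / 0.730 = 76.7%

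The unclassifiable share is (1 − f)q. At p = 1% that is 0.9 × 3.9% = 3.5 per 100 patients for a 4-item Knee Score, and 6.1 per 100 if all seven elements count.

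The two extreme assignments bracket the truth. At q = 0.07, counting all unclassifiable patients as failures gives 0.80 × 0.93 = 74.4%. Counting them all as successes gives 74.4% + 0.9 × 7% = 80.7%.

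**5. Effect of a half-answered rule.** A 7-item same-format scale would be lost only if four or more items were blank, which has probability 0.019% even at p = 5%. This gain does not extend to the AKSS, whose elements are of different kinds.

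**The case against.** A reader might infer that one blank removes the whole questionnaire, and with it every clinical outcome. The text does not support that. It voids the total for that scale, the pain component in 6.1.1 stands when another item is blank, and revision, radiographic and RSA outcomes are not questionnaire scores. The 36-item row above applies only if the whole SF-36 were one scale, which 9.2 does not say.

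A reader might also infer that patients with poorer function leave more blanks and so bias the comparison. The documents give no evidence of this. Section 6 lists the AKSS apart from the patient questionnaires, and it includes examination findings such as motion, stability and alignment. Section 5.5 has a physiotherapist obtain the questionnaires at visits, and only the patient questionnaires are self-completed. The downward drift in step 4 does not depend on such a mechanism.

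Sections 10.2 and 10.3 require complete case report forms, explanations for blanks and clarification queries. These should lower the blank rate. They record and query a blank, but a later query cannot reliably recover a self-reported answer, and neither section restores the score.

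The strongest remaining argument is that a strict rule is pre-specified and transparent, and that scoring from answered items is itself a form of imputation. Both points stand. They are why 9.2's first sentence must carry the exception openly and why the strict rule should be kept as a sensitivity analysis. It is also true that prorating the mixed AKSS items could produce a Knee Score with pain unrecorded, so the half-answered rule should not be applied there.

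**Conclusion.** The point holds as a weakness in secondary analyses. Section 9.2 discards answered items, and nothing elsewhere in the plan offsets this. The loss is modest on short scales at blank rates of 1% or less and becomes material at 2% to 5% or on longer scales. All these figures rest on assumed, independent blank rates.

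In section 6.1.3 the asymmetry follows from the wording itself. Its effect is small in the cases worked: under one percentage point at 7% of scores lost and about three points at 30%, assuming 10% non-score failures, voiding unrelated to outcome, and omission of unclassifiable patients. The missing rule matters more than the size of the drift. The change should be made, but the primary wear comparison does not depend on it.

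**What to change.** Amend both sentences of section 9.2. Keep the first as the general rule and attach this exception in place of the second:

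> *except that a multi-item scale whose items share one response format (e.g. each SF-36 scale, not the 36-item form) is scored from the answered items, rescaled, if at least half are answered. AKSS pain, knee and function scores are computed separately, and each is missing only if one of its own items is blank. Analyses are repeated with the strict any-item rule.*

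Add a short list stating, for each instrument including EQ-5D and LEAS, what a scale is and which rule applies.

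In section 6.1.3, add that patients with a missing Knee Score who meet all other criteria are reported as not classifiable, with sensitivity analyses counting them all as success and then all as failure.

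The cost is a few sentences and simple programming. The downside is the assumption that answered items represent the few unanswered ones in the same scale. The Knee Score keeps a strict rule on its own items, so on the assumed four-item split it would still be lost in 2.0% to 18.5% of forms over the range above. The not-classifiable category and its two sensitivity analyses are there for those patients.

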9.3. Protocol Deviations

Any deviation from this protocol will be recorded with an explanation for the deviation and reported to Stryker who is responsible for analysing them and assessing their significance. Protocol deviations will be reported to the METC according to the local METCs reporting procedures.

Protocol Deviations for this study include the following:

- Informed consent process is not carried out according to ISO 14155 Part 1.
- Subject enrolled does not meet the inclusion/exclusion criteria.
- Subject is not implanted with study device.
- Subject not seen in the specified follow-up window.
- Surgical protocol not followed.

If the site anticipates a possible protocol deviation, the investigator or study coordinator should contact Stryker for guidance. For the examples cited above, it is likely that the patient would be excluded, and a Study Termination form completed.

10. Quality Management

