4.3.1 Specific Criteria for Withdrawal /Termination

In the event that a subject is discontinued from the study for any reason, the site will complete a Study Termination form. Subjects may be withdrawn for the following reasons:

- Patient failure – defined by the requirements at the two- year follow-up interval see section 6.1.3.
- Any Serious Adverse Event that effects the outcome of the study
- Any Serious Adverse Event related to the test device
- Revision/Removal of study device
- Patient withdrawal (patients own request)
- Lost to Follow-Up

- If, in the Investigator's opinion, continuation in the study would be detrimental to the subject's well being (a written explanation is required)
- Completion of study and final evaluation
- Death of the subject

If the patient fails to return for their follow-up appointments, every effort should be made to contact the subject to assess their health status. If after attempting to contact the patient through 3 documented phone calls and a certified (i.e., return-receipt) letter, the patient still does not respond, the patient will be considered as "lost to follow-up". A Study Termination Form will be completed after notifying Stryker of the patient's status.

In the event that the subject is discontinued by the investigative site prior to the final study evaluation, the subject is notified that they are no longer in the study and a Study Termination form will be completed.

Following discontinuation, the subject will be seen regularly as considered clinically appropriate. If the discontinuation was caused by an adverse event the subject will be seen regularly until the symptoms have disappeared or are under control, or until feasible treatment has been undertaken. Refusal to participate or early withdrawal from this investigation will not affect the quality or availability of the subject's medical care.

Subjects withdrawn from the study will keep their subject number. New subjects must always be assigned a new subject number. In the event that the subject withdraws from this investigation, the information that has already been collected will be included in the database and in the final analyses. The subject's medical records will also be available for monitoring, auditing and inspection purposes.

After withdrawal subjects will not be replaced to the study.

5. Subject Enrolment

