5.3. Randomization, Blinding and Treatment Allocation

The patients will be randomized to receive N2Vac polyethylene inlay or the X3 polyethylene inlay (see section 3.3). The randomization will occur via a random number generator (manual or computer). The doctor or other health care professional does not choose the participants for each group. For patients satisfying inclusion criteria, randomisation will occur by retrieving the next randomly generated group assignment. The patient, physiotherapist (for the clinical evaluation) and data analyzers (RSA data, clinical data, radiographic data and statistics) will be blinded. The PI and other participating surgeons have no influence on the collection of the (clinical) data and the data analysis.

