9.1. Statistical Methods

Continuous outcome variables and their differences will be analyzed with parametrical statistical techniques, such as t-tests, unless the normality assumption does not seem reasonable for the data, in which case non-parametric techniques will be considered e.g. Wilcoxon/Mann-Whitney tests.

Categorical outcome variables will be analyzed with chi-square tests and/or Fisher's exact tests (depending on the expected values in the categories). For the relevant parameters (subsidence, survival, pain and function) also the 95 percent confidence intervals will be calculated.

The effect of parameters such as age, sex and operators will be evaluated using multiple variate analysis. All data will be analyzed by blinded researchers.

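### Section 9.3 would likely exclude and terminate patients for deviations arising after randomisation, with no stated decision-maker, no criterion blind to allocation and no as-randomised analysis set

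*Combined protocol and SAP*

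**What the plan says.** Section 9.3 names five deviations: a faulty consent process, an ineligible subject, no study device implanted, a missed visit window ("Subject not seen in the specified follow-up window") and a surgical protocol not followed. Deviations are "reported to Stryker who is responsible for analysing them and assessing their significance". The section ends: "For the examples cited above, it is likely that the patient would be excluded, and a Study Termination form completed".

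Other sections bear on this:

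- **4.3.1** ties the form to leaving the study: "In the event that a subject is discontinued from the study for any reason, the site will complete a Study Termination form". Its list of reasons does not include a protocol deviation, but does include "Completion of study and final evaluation". It keeps, for the final analyses, data already collected from a subject who withdraws, and it rules out replacement.
- **9.2** rules out imputation.
- **3.3** separately removes from the study any randomised patient whose surgeon departs from the allocation because of findings at operation.
- **5.3** blinds the patient, the physiotherapist and the "data analyzers (RSA data, clinical data, radiographic data and statistics) will be blinded". Section 9.1 adds: "All data will be analyzed by blinded researchers".
- **Section 2** sets the primary comparison as wear after 5 years.

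Sections 9.1 to 9.3 define no analysis population, whether as-randomised, intention-to-treat or per-protocol.

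**The concern.** Randomisation protects the comparison only if the patients compared are those who were randomised, or if any departures from that set are unrelated to allocation and outcome. Section 9.3 makes removal the expected response to events that happen after randomisation. It hedges that response with a likelihood, leaves its scope open and does not tie it to a rule applied blind to allocation. With no as-randomised set to fall back on, membership of the 5-year wear comparison can turn on case-by-case judgement.

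Two things are at stake: selection, if removals differ between arms in a way related to wear, and loss of 5-year measurements that could have been obtained. A late visit or a departure from surgical technique does not in itself prevent wear from being measured.

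**Working it through.** **1. Which deviations follow randomisation.** Section 3.3 places randomisation on the day before surgery. Consent and eligibility concern enrolment. The device and surgical-protocol deviations occur at operation, and the window deviation occurs at a follow-up visit. So three of the five are post-randomisation.

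**2. When removal could depend on wear.** Section 6.3 takes the discharge radiograph, 4 to 7 days after surgery, as the RSA baseline. The two operative deviations precede any wear data, so an exclusion decided at that time cannot depend on observed wear. It could still depend on allocation, since surgeons are not on the blinded list in 5.3. Only the window deviation arises once RSA follow-up has begun.

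**3. What exclusion does to the 5-year value.** There are three cases:

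- *Patient leaves follow-up before year 5 and earlier data are kept.* No 5-year value is ever obtained. With no replacement (4.3.1) and no imputation (9.2), the patient drops out of the 5-year comparison.
- *The 5-year visit itself is out of window.* The value exists. Section 4.3.1 suggests keeping it, but speaks of subjects who withdraw and not of those excluded under 9.3.
- *Exclusion from analysis.* Values already collected would be lost too. Nothing in 9.3 rules this out, but pairing exclusion with the termination form makes it the less natural reading.

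The form does not settle the matter. Section 4.3.1 requires it for any discontinuation and counts normal completion among its reasons, so completing one says nothing about removing data.

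**4. Power.** Inputs from section 3.2: difference 0.1 mm, SD 0.1, two-sided alpha 0.05, two-sample t-test, 27 per group for 95% power, 50 per group recruited. I take the difference and SD to be on the same time scale, so the standardised difference is 0.1/0.1 = 1. Power comes from the noncentral t distribution with noncentrality 1 × √(n/2) and 2n − 2 degrees of freedom.

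- n = 27: √13.5 = 3.67, 52 df, power 95.0%. The plan's figure is reproduced; n = 26 gives 94.2%.
- n = 50: √25 = 5.00, 98 df, power 99.9%.
- Loss needed to fall from 50 to 27: 1 − 27/50 = 46%, or 23 patients per group.
- Assumed exclusion of 10, 20, 30 or 40%, unrelated to outcome, leaves 45, 40, 35 or 30 per group, with power 99.7, 99.3, 98.5 or 96.8%.

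The documents give no exclusion rate, so these percentages are a range and not a forecast.

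**5. Bias.** Its size would depend on how many patients are removed in each arm and how removal relates to wear. The documents give neither, so no figure can be computed.

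**The case against.** The strongest reply is that 9.3 is milder than it looks. The sentence directly follows advice to sites that anticipate a deviation, so it may be guidance on planned departures and not a rule for discarding measured data. Section 4.3.1 points to exit from follow-up with data kept. RSA analysis is done by a CRO, the analysts are blinded, and 5.3 says the surgeons have no influence on data collection or analysis. Two of the three post-randomisation deviations occur before wear can be seen.

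Most of this stands, and it rules out several stronger readings:

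- *That an unblinded sponsor decides who is excluded.* The sponsor judges the significance of deviations, but the exclusion sentence names no one, and 4.3.1 also speaks of discontinuation by the site. The documents do not say whether the sponsor's assessor is blinded.
- *That measured wear data will be thrown away.* The text permits this reading but does not favour it.
- *That the result will be biased, or the error rate inflated by some amount.* That needs an assumed pattern of selective removal for which the documents give no basis.
- *That the trial will be underpowered.* The margin from 50 to 27 per group argues against this.

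The reply does not close the gap. The sentence covers the listed examples without limiting itself to anticipated ones. Keeping earlier data does not supply a 5-year value that was never measured. Blinded analysts can work only with the patients who remain.

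**Conclusion.** The point holds as a matter of avoidable risk and incomplete specification. Followed as written, 9.3 would likely end participation for some randomised patients because of post-randomisation events, at the cost of their 5-year wear values. No decision-maker, no criterion blind to allocation and no as-randomised set governs this, and 3.3 adds a second post-randomisation exclusion.

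The documents do not show that bias will occur, and its size cannot be computed from them. The planned sample size is unaffected: 95.0% power at 27 per group and 99.9% at 50, assuming a standardised difference of 1. The conclusion rests on reading 9.3 as applying to all five listed deviations and on the likelier meaning of exclusion as exit from follow-up. If it means removal from analysis, the problem is greater. It is worth correcting because the change is cheap.

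**What to change.** Replace the last sentence of 9.3 with: *Out-of-window visits and departures from the surgical protocol are recorded and reported but do not by themselves lead to exclusion from follow-up or from analysis. The primary analysis includes all randomised patients with wear data, in their allocated group, whatever their deviations.*

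In addition:

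- State in 4.3.1 that data collected before any termination, including a 5-year wear value, stay in the analysis.
- Report by arm, with reasons, all patients excluded or terminated before year 5, including those removed under 3.3.
- Use a per-protocol set, fixed blind to allocation and RSA results, as a sensitivity analysis only.
- Handle invalid consent under the ethics committee's requirements.
- Reconcile 9.3 with 3.3 and 4.3.1, stating what exclusion means and who decides it.
- Keep the planned two-group comparison as primary. Any use of actual visit time is an optional sensitivity analysis and should let wear rates differ by arm, since the trial expects them to differ.

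The cost is protocol wording, one by-arm table and one sensitivity analysis, with no change in sample size. The downside is that the primary estimate will include a few patients with imperfect adherence or off-schedule measurements.
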